## **7. Feedback to participants and the Wider Community**

**7.1 Individual based:** Participants will be asked at the time of entry to the study whether they would wish to be informed if the project discovers they have a genetic mutation related to PD that has a validated NHS genetic test. If they elect to be informed, they will be contacted by letter. This will allow the individual to seek formal NHS (or equivalent) neurogenetics disease gene confirmation via an accredited genetics service and for potentially at risk family members to seek predictive counselling and testing via an NHS clinical genetics service if they wish. It will be emphasized that research results cannot be used for diagnosis or genetic counselling but that the appropriate NHS services will be used and that we will link closely with normal NHS care. The main genetics services with which we will work will be the Neurogenetics clinic, National Hospital for Neurology and Neurosurgery and Royal Free Hospitals. Where an individual does not want feedback, no communication of specific research findings will be made.

Participants will also be asked at time of entry into the study whether they would consent to be re-contacted based on results (genetic or biochemical) generated from this study should these results indicate they would be eligible for new research studies or therapies for

Parkinson's disease. The contact will involve providing information about new studies with no commitment to enter these studies.

**7.2 Incidental identification of health problems:** There is the potential to detect unexpected, unrelated pathology in individuals undergoing clinical evaluation and clinical test. In such a case, the clinical research team will discuss the situation with the study participant and advise they see their GP to discuss whether specialist referral to assess and potentially treat these symptoms is appropriate. Relevant results will also be fed back to the participant's GP with their consent. This possibility will also be made clear in the consent form signed by the study participant.

**7.3 Scientific publication of results:** will be via written reports to scientific journals. These publications will involve publication of anonymized information in scientific journals and the results of the research listed above.

## **8. Adverse events**

All adverse events will be recorded in the case records. Adverse events may include side effects from the assessments performed but may also include signs or symptoms that may or may not be related to the study procedures. Appropriate local procedures will be in place for reporting of adverse events.

**8.1 Reporting Serious Unexpected Adverse Events:** All Serious Unexpected Adverse Events to a research subject in the study must be reported immediately to the sponsor using the following email address [[contact]](mailto:[contact]).

A Serious Adverse Event

- Results in death
- Is life Threatening
- Requires Hospitalisation or prolongation of hospitalisation
- Results in persistent or significant disability or incapacity
- Consists of a congenital anomaly or birth defect
- Any other serious medical occurrence

Serious Adverse Events will be documented from the point of enrolment until the patient is exited from study. Information recorded and reported shall include

- A description of the event
- The date of event onset
- The relatedness of the event to the procedure
- The expectedness of the event
- The outcome of the event
- The date the event was first noticed by, or reported to the investigator

All ongoing Serious Adverse Events will be followed-up until the last study visit.

**8.2 Reporting Incidents:** All incidents must be reported through the appropriate Trust incidents reporting system. Where no Trust is involved the incident should be reported by completing form at <http://www.ucl.ac.uk/jro/postapproval>

Where the study is being conducted at UCLH then the incidents should be reported through Datix.

An incident in a research study is

- Something that should not have happened OR
- Something that should have happened but didn't

Which significantly effects any of the following

- The rights and well-being of the research subject
- The scientific value of the study
- The compliance of the study with all relevant legal rules or ethics guidance including the Data Protection Act and the Human Tissue Act.
- The reputation of UCL

This includes a requirement to report all serious breaches of protocol or GCP (if applicable).

## **9. Data and sample management**

**9.1 Storage of data:** Patient identifiable source data will be stored in clinical subject folders in locked cabinet/locked room at study centres. Electronic scanned copies of primary consent forms and primary NHS records (e.g. NHS copy clinic letters, discharge summaries, previous genetic tests and scans) will be stored on the main NHS data store or on the secure database. Personally identifiable data will be transferred by mail, fax or 256-AES encrypted digital communication.

Participants will have a unique study ID generated using a standard labelling procedure. A 'code-break' will exist on the secure network if the need to identify a patient is required. Only the study primary investigators ([name] and [name]) and the study co-ordinator ([name]) will have access to this 'code-break'.

The main study database will be held in pseudo-anonymised form (study number) on a web application called REDCap, which is PHP software with a MySQL database back-end, created by Vanderbilt University for creating and managing online databases and surveys. It is tried and tested and popular among research institutions particularly for use in managing clinical studies and trials, longitudinal studies and surveys. REDCap has password protected and granular access to data and software modules, as well as logging and audit trails of any activity. It enforces a robust security model, with password requirements/expiry and time-outs, and any communication is encrypted through SSL. The database will be on a Linux server virtual machine hosted on a secure cloud hosting service. The web host, network connection and storage is Information Governance Toolkit compliant and ISO27001 certified following data security best practice. The database server will be backed up to two separate locations with server redundancy, meaning if one server goes down then a mirror will be up instead. No patient identifiable data will be held on this web based system.

Personally identifiable information will be held on a database which is separated from the main study database, with access restricted to the study coordinator and chief investigator.

The Study Coordinator will be responsible for enforcing a secure and robust system for maintaining coherent de-identified participant IDs at the central database.

Study clinical and genetic data will also be stored in pseudo-anonymised form with study code number on University (UCL) computer systems or other secure database.

Anonymised data with study code and year of birth may be shared with external collaborators as indicated above. Participants' personal data, including their name, postcode, date of birth and NHS number will be shared with the NHS Health and Social Care Information Centre in order to provide information about their health status. Storage and handling of data will follow Standard Operating Procedures. The databases will be maintained until 2037 for genetic/epidemiological research, under the custodianship of [name] or [name] to enable the long term follow up of participants recruited in this study. It may become important for participants to be re-contacted if new treatments or NHS tests become available as a result of this research.

**9.2 Archiving:** UCL recognises that there is an obligation to archive study-related documents at the end of the study (as such end is defined within this protocol). The Chief Investigator confirms that he will archive the study master file at Royal Free for the period stipulated in the protocol and in line with all relevant legal and statutory requirements. The Principal Investigator agrees to archive the site's study documents for **10 years** following the study end, and in line with all relevant legal and statutory requirements.

At the end of the research all existing biosamples from the study will be transferred to the Clinical Neurological Disorders DNA and Serum Research Bank (CANDAS) at UCL, under the custodianship of [name] (co-principle investigator of this study).

**9.3 Sample handling:** Plasma, serum, urine, CSF and peripheral blood lymphocytes (PBLs) will be stored in secure freezers at the Royal Free Hospital Clinical Neuroscience Laboratories; Royal Free Hospital Biobank or National Hospital for Neurology Neurogenetics Laboratory.

**9.4 Blood/DNA/RNA:** will be extracted and then stored in a local or collaborating DNA/RNA lab (e.g. Institute of Neurology Neurogenetics lab, Department of Clinical Neuroscience Laboratory Royal Free Hospital) and/or processed at the European Consortium for Cell Cultures (ECACC), Salisbury, Wiltshire.

**9.5 Cell lines:** will be stored at Royal Free Hospital Clinical Neuroscience Laboratories; Royal Free Hospital. Cell lines may be submitted for bio-banking at ECACC (see section 6.2), StemBANCC, and collaborating laboratories in the UK and worldwide.

StemBANCC is a large-scale international multi-site partnership in the area of stem cell research. It brings a consortium of 35 partners together who share their experience in the field. It is a resource for developing new disease models and testing new therapies, funded by several partners including the UK Medical Research Council. It is a consortium which includes UCL and is overseen by a Scientific Ethical and Advisory Board and managed by [name], University of Oxford.

**9.6 Quality assurance:** An ongoing record of completion of study procedures will be kept. Protocol changes and personnel changes will be notified to REC, Local Trusts and other appropriate organizations.

**9.7 Insurance:** University College London holds insurance against claims from participants for harm caused by their participation in this clinical study. Participants may be able to claim compensation if they can prove that UCL has been negligent. However, if this clinical study is being carried out in a hospital, the hospital continues to have a duty of care to the participant of the clinical study. University College London does not accept liability for any breach in the hospital's duty of care, or any negligence on the part of hospital employees. This applies whether the hospital is an NHS Trust or otherwise

## **10. Training**

The Chief Investigators will review and provide assurances of the training and experience of all staff working on this study. Appropriate training records will be maintained in the study files. Written Informed consent will be obtained by individuals trained in GCP. MDS-UPDRS assessment will only be carried out by those trained to do.

## **11. Intellectual property**

Intellectual property agreements have been agreed regarding this project, see section 8 (page 18) of signed final version of consortium agreement for the project 'SysMedPD'.

## **12. Supply of equipment**

UCL owned research equipment (e.g Department of Clinical Neuroscience video recorder) will be used.

## **13. Statement of Compliance**

The Chief Investigators will ensure that this study is conducted in accordance with the principles of the Declaration of Helsinki and in full conformity with relevant regulations and with the ICH Guidelines for Good Clinical Practice (CPMP/ICH/135/95) July 1996

### **Sample size**

As this part of a multi-site European project statistical review was conducted before submission for EU funding by the lead site (University of Luxembourg). A prospective analysis of the power of the univariate Wilcoxon-Mann-Whitney test was performed. With a total sample size of 120, the power to detect an effect size of 0.5 at a significance level of 0.05 is 0.8 (80%). As such a sample size of 160 should be sufficient to detect meaningful differences as well as have some contingency for patient drop out and anomalous/outlier results that need to be excluded from analysis.

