### **Statistical analysis**

1. Comprehensive phenotyping data for the monogenic PD cohort with age and sex matched controls will be used to define a phenotypic signature of monogenic PD with detectable a specific biochemical signature e.g. mitochondrial dysfunction. Phenotyping data will include measurements of metabolites in patient biosamples, biochemical assays of mitochondrial function and clinical data. Standard statistical methods will be used to select the most informative phenotypic assays. Statistical analysis will include univariate and multivariate statistics such as principal component analysis, linear mixed models, partial least squares regression, ANOVA simultaneous component analysis, Lasso shrinkage, and selection method for linear regression.
2. The most informative of the above phenotypic assays will be used to define a biochemical signature for mitochondrial dysfunction in PD. This signature will be used to then stratify idiopathic PD patients by their degree of mitochondrial dysfunction. Those patients who lie at the 'ends of the spectrum' of these pathways (least and most affected) will then have advanced cell models (such as iPSC derived dopaminergic neurons) generated from skin biopsy samples to further study biochemical pathways affected in PD. In the first instance those participants who lie 1 standard deviation outside the control mean of the most informative assays will be considered as those that lie at the 'ends of the spectrum'.

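### The SAP's 80% power is for one test in 120 participants and does not describe the assay-selection step, which compares about 30 with about 30 over an unstated number of measures under no stated error control

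*SAP*

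**What the plan says.** **SAP, Sample size.** The justification is a single calculation: "A prospective analysis of the power of the univariate Wilcoxon-Mann-Whitney test was performed". Its inputs are "With a total sample size of 120", "the power to detect an effect size of 0.5" and testing "at a significance level of 0.05", which give 80% power. The section does not give the sidedness, the split of the 120 between groups or the type of effect size. It concludes that "a sample size of 160 should be sufficient to detect meaningful differences", with some allowance for drop-out and excluded outliers.

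**SAP, Statistical analysis, item 1.** The monogenic PD cohort and age- and sex-matched controls are used to define a signature. The candidates are "measurements of metabolites in patient biosamples, biochemical assays of mitochondrial function and clinical data". The selection rule is: "Standard statistical methods will be used to select the most informative phenotypic assays". Univariate statistics are named, along with principal component analysis, linear mixed models, partial least squares, ANOVA simultaneous component analysis and Lasso.

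**SAP, Statistical analysis, item 2.** The selected assays define the signature that stratifies idiopathic PD, and they identify the participants at either extreme whose skin biopsies become advanced cell models.

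**Protocol, section 5.** The 160 participants are 100 with idiopathic PD, 30 with genetic forms and 30 healthy controls.

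Neither document states the number of candidate measures, a level for declaring an assay informative, a family-wise or false-discovery rate, or a validation step for the selection.

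**The concern.** The power calculation and the analysis it supports concern different comparisons. The calculation takes one test and 120 people. Selection takes many measures and about 60 people in two groups of 30. A reader of the sample-size section would conclude that the study has an 80% chance of finding an assay that differs by 0.5, and at the selection step it does not.

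Two things are at stake. Informative assays may be missed because the groups are small. Uninformative assays may also be selected by chance, since nothing in item 1 limits this. The selected assays set the mito-PD and amito-PD labels and determine which idiopathic participants' cells are developed further, so an error in item 1 carries into item 2. Stratification is the study's main overall objective (Protocol, section 3.1).

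**Working it through.** **Inputs**
- From the SAP, Sample size: Wilcoxon-Mann-Whitney test, total 120, effect size 0.5, level 0.05, power 0.80.
- From the Protocol, section 5: 30 monogenic PD, 30 controls, 100 idiopathic PD.
- Assumed: the effect size is a standardised mean difference d with normal data; all 30 and 30 contribute; the number of assays m is 5, 20 or 100, because no figure is given.

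**Formula.** Multiply the group sizes by the test's efficiency relative to the t-test, A = 3/π = 0.955 under normality. The noncentrality is d × √(A × n1 × n2 / (n1 + n2)), and power comes from the noncentral t distribution with A × (n1 + n2) − 2 degrees of freedom.

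**1. The plan's own figure.** At 60 v 60 the noncentrality is 0.5 × √(0.955 × 30) = 2.68.
- Two-sided: 0.756 (a simulation of 40,000 runs gives 0.755). A total of 134 would be needed for 80%.
- One-sided: 0.845.
- One-sided with the lower-bound efficiency 0.864: 0.812, with a minimum total of 118.
- One-sided with an 80/40 split: 0.806.

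The stated 0.80 is therefore reproduced on one-sided readings with choices that the SAP does not state.

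**2. The comparison used for selection, one assay, no adjustment.** At 30 v 30 the noncentrality is 0.5 × √(0.955 × 15) = 1.89.
- Two-sided: 0.46. One-sided: 0.59.
- The effect detectable with 80% power, two-sided, is about 0.75.

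This step needs no assumption about panel size. The other contrasts with the control group also fall short of 80% unadjusted: 100 v 30 gives 0.64 two-sided (0.75 one-sided), and 130 v 30 gives 0.67 (0.78).

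**3. Several assays.** Two-sided, d = 0.5, Bonferroni level 0.05/m:

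| m (assumed) | level | power, 30 v 30 | power, 60 v 60 | effect detectable with 80% power, 30 v 30 |
|---|---|---|---|---|
| 1 | 0.05 | 0.46 | 0.76 | 0.75 |
| 5 | 0.01 | 0.23 | 0.52 | 0.93 |
| 20 | 0.0025 | 0.11 | 0.34 | 1.07 |
| 100 | 0.0005 | 0.05 | 0.19 | 1.21 |

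Simulated power at 30 v 30 agrees to within about 0.01 (0.22, 0.10 and 0.04 for 5, 20 and 100).

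Bonferroni is the conservative end. Simulating Benjamini-Hochberg at 5% with 20 independent assays at 30 v 30 gives average power of about 0.13 to 0.18 when 20% to 50% of the assays are truly different. A Benjamini-Hochberg cut-off at 5% never exceeds 0.05, so 0.46 is a ceiling for two-sided per-assay power there.

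**4. Chance selections if 0.05 per test were used.** With m independent null assays, the expected number is 0.05 × m and the chance of at least one is 1 − 0.95^m.
- m = 5: 0.25 expected; 1 − 0.95^5 = 23%.
- m = 20: 1 expected; 1 − 0.95^20 = 64%.
- m = 100: 5 expected; 1 − 0.95^100 = 99%.

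**The case against.** A reader might infer that the plan screens at an unadjusted 0.05 and that this level is wrong. The documents do not say so. The 0.05 appears once, as an input to the power calculation, and item 1 sets no level at all. The false-selection figures in step 4 are therefore conditional. They also assume independent assays; positive correlation among metabolite and mitochondrial measures would typically lower the chance of at least one false selection.

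A reader might also infer that the 80% is a miscalculation. It is labelled univariate and is reproduced on one-sided readings, so the criticism is of what it is used for.

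Three further points stand.
- Lasso and partial least squares do not select by per-test p-values, and the most informative assays could be found by ranking. Error control on univariate tests alone would leave overfitting on that route untouched.
- Bonferroni overstates the loss under false-discovery control, most of all for large panels. Power under Benjamini-Hochberg depends on the share of true effects as well as on panel size.
- Much of the shortfall at 30 v 30 comes from group size: power is already 0.46 before any adjustment.

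This is also a basic-science study. The protocol describes the cell models as a means of validating initial findings, all monogenic biopsies become models whatever the screen shows, and cohort membership is not to change care. These facts limit the consequences. They do not supply a selection rule, and the later cell work does not control which assays are chosen.

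**Conclusion.** The concern holds as a mismatch and an omission. The stated 80% belongs to one test in 120 participants. The selection step has power of about 0.46 two-sided for a single unadjusted assay, and less under any multiplicity control. This rests on reading the effect size as a standardised mean difference, on approximate normality and on full use of both groups of 30. The figures for several assays rest in addition on assumed panel sizes and show a range only. The omission needs no assumption: the SAP states no panel size, selection level, error control or validation for a step on which the stratification depends.

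**What to change.** **SAP, Sample size.** State that the 80% applies to a single test in 120 participants and not to assay selection, and add the sidedness, group split and type of effect size. Give the power or detectable effect for 30 v 30, both for one assay and for the planned panel size. Use Bonferroni as the conservative bound, or Benjamini-Hochberg with a declared share of true effects.

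**SAP, Statistical analysis, item 1.** Where assays are selected by univariate test, require Benjamini-Hochberg false-discovery control (for example at 5%) across all assays tested in monogenic PD v controls, and report the number tested and the adjusted p-values. Where Lasso or partial least squares is used, require cross-validated selection.

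**Cost.** Wording and a routine calculation. The power statement becomes less favourable and fewer assays will be declared informative. No extra recruitment is needed.

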#### **4. Objectives**

To identify participants with known monogenic forms of PD and related disorders (PINK1, parkin, GBA, LRRK2) for biochemical assessment of blood, urine, CSF and tissue samples to identify defects in specific biological pathways (e.g. mitochondrial dysfunction). The most informative of these assays will then be applied to participants without genetic mutations (IPD) to stratify them based on dysfunction in these biochemical pathways.

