#### **5. Study design**

It is planned that 160 participants will be recruited to the study (comprising 100 with idiopathic Parkinson's disease, 30 with genetic forms of Parkinson's disease and 30 healthy control subjects). This is based upon power calculations conducted by the University of Luxembourg (who constructed the initial EU study proposal).

Participants will be asked to take part in up to 3 visits, one at baseline where a full assessment including clinical assessment and biosamples donation will take place, an optional visit for skin biopsy and/or CSF sampling and one further visit 1-2 years post entry into the study for repeat assessment and biosamples collection for participants with PD only. Data and samples will be collected in a standardised format and, following site based subject anonymization, will be entered onto a secure web-based database. To develop a patient registry, subjects can provide consent for permission to be contacted if further/additional research projects were to become available.

All participants must consent to the core protocol of clinical assessment and blood and urine donation. CSF and skin biopsy consent is highly desirable but optional. Skin biopsies will be requested from some study participants including unselected PD patients, healthy controls and PD patients with defined genetic and/or biochemical phenotypes. If participants are identified as being in particular cohorts of interest post baseline assessment/sampling analysis (e.g. the mito-PD or amito-PD groups) then cell lines generated from skin biopsies from these participants will be used to create advanced cell models, such as induced pluripotent stem cells and dopaminergic neurons for further biochemical analysis and validation of initial findings. All monogenic PD participant skin biopsy samples will be used to generate such models.

Patients will be asked if they want to be informed of the availability of NHS genetic or biochemical tests which emerge as a result of this research. Participants will not be made aware of the cohort they fall into as currently this will not change their medical care, however consent will be sort to re-contact patients based on the results of this study if these results suggest they will be eligible for novel therapies for PD or would be eligible to take part in future studies or clinical trials related to Parkinson's disease. Control subjects will be asked to

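### The 80% power quoted for a total of 120 does not describe the planned groups: the signature-building step, 30 monogenic PD against 30 controls, has about 46% power for a 0.5 SD difference

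*SAP*

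**What the plan says.** The SAP's Sample size section names the method: "A prospective analysis of the power of the univariate Wilcoxon-Mann-Whitney test was performed". For a total of 120 it states that "the power to detect an effect size of 0.5 at a significance level of 0.05 is 0.8 (80" per cent). It then infers: "As such a sample size of 160 should be sufficient to detect meaningful differences", and adds that this total will "have some contingency for patient drop out and anomalous/outlier results". It gives no group names, allocation ratio, sidedness, effect-size metric or distribution.

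Protocol section 5 divides the 160 into 100 participants with idiopathic PD, 30 with genetic PD "and 30 healthy control subjects", and ties that recruitment to the same calculation: "This is based upon power calculations conducted by the University of Luxembourg".

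SAP, Statistical analysis, item 1 describes the first step: "Comprehensive phenotyping data for the monogenic PD cohort with age and sex matched controls will be used" to define the signature. Protocol section 4 describes what follows: "The most informative of these assays will then be applied to participants without genetic mutations (IPD").

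**The concern.** The power of a two-group test depends on the sizes of the two groups compared, not on the total enrolled. A figure for an unspecified split of 120 is used to justify a three-group design of 160 in which the first comparison involves only 60 people.

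This is the only quantitative justification for the sample size in either document. The plan is also sequential: assays are selected in the monogenic step and then used to stratify the idiopathic patients. An informative assay missed in the first step cannot enter the signature. On the SAP's own yardstick that step has the least power, yet a reader would take it to have 80% with room for losses.

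**Working it through.** **Inputs.** From the SAP (Sample size): Wilcoxon-Mann-Whitney test, total 120, effect size 0.5, significance level 0.05, power 0.80. From protocol section 5: groups of 100, 30 and 30. Assumed, because not stated: effect size is a standardised mean difference (0.5 SD). Both one- and two-sided tests are shown, for three distributional cases.

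**Formula.** Wilcoxon power is approximated by the noncentral t distribution, with each group size multiplied by the asymptotic relative efficiency (ARE): 3/π = 0.955 for normal data, π²/9 = 1.097 for logistic data, and 0.864 as the minimum. The noncentrality is δ = d × √(ARE × h), where h = n₁n₂/(n₁+n₂).

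**Step 1: the SAP's own figure.** At 60 vs 60, h = 30. For normal data δ = 0.5 × √(0.955 × 30) = 2.68, giving two-sided power 0.756. Logistic data give 0.812 two-sided, and the minimum-efficiency case gives 0.812 one-sided. So 0.80 at a total of 120 is attainable under some standard assumptions and is not shown to be an error.

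**Step 2: match to the planned groups.** The pairs of planned groups total 30 + 30 = 60, 100 + 30 = 130 and 100 + 30 = 130. None is 120, and only one group reaches 60. For 30 vs 30, h = 900/60 = 15. A total of 120 gives h = 15 only if n₁(120 − n₁)/120 = 15, that is n₁ = 60 − √1800 = 17.6, a split of about 18 vs 102. Nothing in the plan matches that.

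**Step 3: power for the planned groups at 0.5 SD.** For 30 vs 30 with normal data, δ = 0.5 × √(0.955 × 15) = 1.89.

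| Groups | Sides | Minimum ARE | Normal | Logistic |
|---|---|---|---|---|
| 60 vs 60 (reference) | 2 | 0.713 | 0.756 | 0.812 |
| 60 vs 60 (reference) | 1 | 0.812 | 0.845 | 0.886 |
| 30 vs 30 | 2 | 0.423 | 0.460 | 0.515 |
| 30 vs 30 | 1 | 0.552 | 0.589 | 0.641 |
| 27 vs 27 (assumed 10% loss) | 2 | 0.386 | 0.421 | 0.473 |
| 100 vs 30 | 2 | 0.600 | 0.644 | 0.705 |
| 100 vs 30 | 1 | 0.717 | 0.755 | 0.805 |

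Simulated Wilcoxon tests agree: for 30 vs 30, two-sided, about 0.46 with normal data and 0.50 with logistic data.

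**Step 4: take the SAP's 0.80 as exact.** This removes the distributional assumption. The implied noncentrality is 1.960 + 0.842 = 2.802 two-sided, or 1.645 + 0.842 = 2.486 one-sided. Rescale it by √(h for the planned groups / h for the assumed split of 120).

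- If 120 means 60 vs 60 (h = 30), 30 vs 30 has 2.802 × √(15/30) = 1.981, so power Φ(1.981 − 1.960) = 0.51 two-sided; one-sided 0.55.
- If 120 means 90 vs 30 (h = 22.5), 30 vs 30 has 2.802 × √(15/22.5) = 2.287, so power 0.63 two-sided; one-sided 0.65.
- For 100 vs 30 (h = 23.1) the corresponding values are 0.69 and 0.70 from 60 vs 60, and 0.81 either way from 90 vs 30.

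**Step 5: detectable effect at 80% power** (two-sided, normal data): 0.75 SD for 30 vs 30, 0.80 SD for 27 vs 27, 0.60 SD for 100 vs 30. About 67 per group would be needed for 0.5 SD.

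**The case against.** The strongest reply is that the SAP never attaches its calculation to the monogenic step. It describes a review for a multi-site European project, and protocol section 6.4 allows samples from collaborators. The stated aim is to stratify PD patients, and a contrast within the idiopathic group, with an assumed 50 vs 50 split, would have 0.68 (two-sided, normal). Step 1 is assay selection with multivariate tools in a basic science study, not a confirmatory test. Monogenic cases may show effects well above 0.5 SD, and a paired analysis of matched controls could gain power.

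Much of this is fair as context. Univariate Wilcoxon power is only a proxy for what the selection step will do, and a detectable effect of 0.75 SD is not shown to be inadequate. But the protocol ties this 160 to this calculation, no additional monogenic or control numbers are stated, the stated test is unpaired, and no within-pair correlation is given. The assumed 50 vs 50 split also falls short of 80% on the same basis.

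Two points about the figures also stand. The central 46% rests on two-sided normal data, which gives 0.756 rather than 0.80 at 60 vs 60; the values calibrated to the SAP's own figure are 0.51-0.65. The 42-64% range is a sensitivity range, and its ends come from cases that give 0.713 and 0.886 at 60 vs 60. Heavier tails (double-exponential data) raise 30 vs 30 to about 0.62 two-sided and 0.74 one-sided, still below 0.80, but would put 60 vs 60 at about 0.90. None of these restores 80% for 30 vs 30.

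Finally, the contingency sentence is about the whole study, and controls attend only at baseline, so later dropout would not affect a baseline comparison. Exclusion of outlying results would.

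**Conclusion.** The concern holds. The SAP's 80% is reproducible for two equal groups of 60 under some assumptions, but the design contains no such comparison. For the step on which the signature rests, 30 vs 30, power for 0.5 SD is about 46% (two-sided, normal data): 42-52% two-sided and 55-64% one-sided across the three distributional cases, and 51-65% if the SAP's 0.80 is accepted as exact. The contingency inferred from 160 against 120 does not reach either group of 30.

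The case is weaker for 100 idiopathic PD vs 30 controls: 64% two-sided with normal data, but about 81% if the 120 meant 90 vs 30.

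These figures assume that the effect size of 0.5 is a standardised mean difference and that the test is unpaired, with no adjustment for screening many assays. Such an adjustment would lower them. An exploratory study may accept this power, but its plan should not lead the reader to infer 80%.

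**What to change.** Keep the total at 160. Replace the power statement with one for the planned comparisons that names the groups, sidedness, effect-size metric and distribution. Possible text, with the assumptions replaced by the lead site's own if they differ:

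> Two-sided Wilcoxon-Mann-Whitney test at 0.05, assuming normal data and effect size as a standardised mean difference, before dropout or exclusions: 30 monogenic PD vs 30 controls has 80% power for about 0.75 SD (46% for 0.5 SD); 100 idiopathic PD vs 30 controls has 80% power for about 0.60 SD (64% for 0.5 SD). With an assumed 10% loss, 27 vs 27 has 80% power for about 0.80 SD.

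If the figure for 120 is retained, say which groups and split it refers to. Limit the contingency statement so that it does not cover the 30 vs 30 step.

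The cost is SAP wording only: no extra participants and no change of analysis. The stated power becomes less favourable.
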